 Brief physical examinations.

 Only at ET

 ECG will be recorded at 0 (pre-dose, within 1 hour of dosing), 1 (± 30 min), and 3 (± 1 hour) hours post-dose on Day 1 and Week 4. ECG will be recorded only once at screening, Week 12, and ET visits.

 If PPD is used, a second screening visit will be necessary.

 Optional, only for a subset of approximately 68 subjects who consent: two 4.5-mm skin biopsies at Day 1 (one from lesional skin and one from adjacent nonlesional skin) and one at Week 12/ET (from lesional skin). Subjects consenting to biopsies collection must also consent to PD samples. Biopsies should be collected prior to study product administration.

 Optional, only for a subset of approximately 68 subjects who consent: PD samples to be drawn as trough samples prior to study product administration. Subjects consenting to PD samples must also consent to biopsies collection. PD samples should be collected prior to study product administration.

 An additional skin biopsy from lesional skin and PD sample will be collected at Week 4 for subjects who consent to four biopsies.

 PK samples will be collected at 0 (pre-dose), 1 (± 30 min), 3 (± 30 min), and 6 (between 5 to 12 hours post-dose) hours post-dose. The dosing time for the previous day should be recorded accurately.

 PK samples will be collected at 0 (pre-dose) and 2 (± 30 min) hours post-dose. The dosing time for the previous day should be recorded accurately. At ET and Week 12, only one PK sample will be collected.

 Follow-up visit for subjects not participating in the OLE study. Subjects who have their study product discontinued due to the start of a prohibited medication for the treatment of AD or for any other safety reasons will be asked to come back for an additional follow-up visit about 4 weeks after the study product discontinuation (in addition to the ET visit). Refer to section 6.4.2 for more details.

 Study products will be taken at home daily for 12 weeks, except on study visit days when the study products will be administered on site. No drug administration will be given at Week 12 visit as part of the present study.

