#### **5.3.1 Discontinuation**

Subjects who discontinue the study after the first dose will be asked, if they agree, to come for a last assessment (ET visit). Subjects who receive an active treatment for AD after Week 4 visit are not necessarily discontinued from the study (refer to section [6.4.2](#) for more information on how to proceed with these subjects). Subjects who have their study product discontinued due to the start

of a prohibited medication for the treatment of AD or for any other safety reasons will be asked to come back for an additional follow-up visit about 4 weeks after the study product discontinuation (in addition to the ET visit).

Subjects who did not complete the study for reasons other than safety, or have demonstrated significant noncompliance to study treatments based on IP accountability (define as subject who received <80% or >120% of the scheduled doses during the study treatment period) will be evaluated by the principal investigator or designee at each visit and may potentially be replaced. If a subject drops out during the first 4-week period, the subject may be replaced at sponsor's discretion.

Reasons for discontinuation include the following:

- The investigator decides that the subject should be withdrawn. If this decision is made because of a serious adverse event (SAE), the study product is to be discontinued in that subject immediately and appropriate measures are to be taken. The investigator will notify the sponsor immediately.
- The attending physician requests that the subject be withdrawn from the study.
- The subject, for any reason, requires treatment with another therapeutic agent may be discontinued as detailed in section [6.4.2](#).
- The subject is lost to follow-up. In this case, a reasonable attempt to contact the subject and ascertain his or her status must be made, and these attempts must be documented.
- The subject becomes pregnant at any time during the study.
- The subject may withdraw from the study for any other reason, including withdrawal of consent.

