3 STUDY DESIGN

3.1 Overall Design

This study will be performed at approximately 50 study centers located in the United States, Canada and Germany.

	STATISTICAL ANALYSIS PLAN, Version Final 2.0
Protocol Number: ASN002AD-201 V3.0	Sponsor: Asana BioSciences, LLC

This study is a randomized, double-blind, placebo-controlled, multicenter, Phase 2b study. Approximately 220 subjects with moderate to severe AD (as defined by a BSA involved with AD of $\geq 10\%$, an EASI ≥ 16 , and an IGA ≥ 3 at Day 1) will be included in this study to complete the study with at least 160 evaluable subjects (all subjects which have completed an EASI score at week 12). Subjects will be men or women, aged 18 to 75 years, inclusive, at the time of consent.

Each subject should read and sign an informed consent form prior to any screening procedures being performed. Subjects who fulfill all of the inclusion criteria and none of the exclusion criteria will be accepted into the study. After a screening period of no more than 30 days (from Day -30 to Day -1), eligible subjects will be randomized (1:1:1:1) on Day 1 to receive ASN002 at 40 mg, 60 mg, or 80 mg, or placebo once daily for 12 weeks. The treatment period will be followed by a 4-week follow-up period for subjects not participating in the open label extension (OLE) study. For scheduled study visits, subjects will come to the study centers on seven occasions: screening, Day 1, Weeks 2, 4, 8, and 12, and Week 16/ ET for subjects not participating in the OLE study.

Efficacy will be assessed by IGA, EASI, SCORAD, BSA, pruritus NRS (daily), and 5-D pruritus scale. Quality of life will be evaluated using POEM and DLQI.

Safety will be assessed by AEs, physical examination, vital signs, 12-lead ECG, and clinical laboratory tests.

Pre- and post-dose PK blood samples will be collected from all subjects on a sparse sampling schedule at Day 1, and Weeks 2, 4, 8 and 12 (or ET visit, if applicable).

[figure not shown]
At selected study centers, in a subset of approximately 68 subjects who consent, PD blood samples will be collected pre-dose on Day 1 and Week 12 (or ET visit, if applicable). PD samples will be obtained from the same subjects who consent to biopsy collection. An additional PD blood sample will be collected at Week 4 in subjects who also consent to four skin biopsies.

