5.4 Windowing Conventions

Statistical Windows have been proposed for the efficacy endpoints of this study:

	D1 (Baseline)	W2	W4	W8	W12	W16
Day	1	14	28	56	84	112
Statistical Window	Latest pre-dose measurement	[D1 post dose (i.e. Day 2); day 20]	[Day 21 – Day 34]	[Day 35 – D62]	[D63-D87]	[D88-End of study]

If there is more than one assessment for a given timepoint and analysis visit, the assessment closest to the target day will be considered. If there is more than one assessment with the same target date, then the scheduled assessment result will be considered.

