5.7 Handling of Retests, Unscheduled Visits, and Early Termination Data

When retests measurements are done, the retest measurement will be considered for the summary analysis. All data from retest visits will be listed.

For safety data, unscheduled measurements will not be summarized in by-visit summary tables or figures. However, data from unscheduled visits will be listed. Early Termination (ET) visit assessments will be summarized as a separate visit in by-visit outputs.

For efficacy data, unscheduled measurements and ET visit assessments will be re-mapped according to the windowing conventions in section 5.4.

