6.3 Interim Analysis and Data Monitoring

No interim analysis is planned for this study. However, unblinded safety data will be generated and reviewed by the DSMB during the study.

The final analyses on efficacy parameters will be done once all patients have finalized their week 12's assessment. All data will be cleaned up to week 12, a soft lock will be performed and final efficacy results will be provided. The efficacy summaries will be updated once the follow-up visit week 16 will be completed, but this will not affect or change any of the final efficacy results.

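### The SAP's Week 12 window closes at Day 87, so a late scheduled Week 12 visit can be relabelled Week 16; the label of the follow-up visit after a safety stop is also left unstated

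*SAP*

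**What the plan says.** SAP 5.4 introduces its day ranges with "Statistical Windows have been proposed for the efficacy endpoints of this study". Week 8 is Day 35 to 62, Week 12 is Day 63 to 87, and Week 16 is "D88-End of study". When several assessments fall in one window, "the assessment closest to the target day will be considered"; a remaining tie goes to the scheduled result. No range depends on whether the subject is still taking study product.

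SAP 5.7 states: "For efficacy data, unscheduled measurements and ET visit assessments will be re-mapped according to the windowing conventions in section 5.4". It is silent on scheduled visits.

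Protocol 5.3.1 and footnote 12 of the Schedule of Events cover subjects whose study product is stopped because of a prohibited AD medication or for safety. In addition to the ET visit, they are "asked to come back for an additional follow-up visit about 4 weeks after the study product discontinuation". EASI is ticked in the Follow-up / ET column. SAP 3.1 says "For scheduled study visits, subjects will come to the study centers on seven occasions" and its list does not include this extra visit.

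SAP 6.2 sets efficacy data to missing after a prohibited medication is started. It has no matching rule for a safety stop without such a medication. On the update after the Week 16 follow-up, SAP 6.3 says "this will not affect or change any of the final efficacy results".

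**The concern.** The primary endpoint is the EASI change at Week 12, so the rule that decides which assessment carries that label must be unambiguous. Two situations are not settled.

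First, a subject who attends the scheduled Week 12 visit a few days late can lose the primary value to the Week 16 label, although the visit is plainly the Week 12 visit. At Week 16 it would also compete with a true follow-up visit nearer Day 112, and lose under the closest-to-target rule.

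Second, for a subject stopped for safety in mid-study, a value taken about four weeks off drug can enter the primary model as Week 12. For a completer, the visit four weeks after treatment is Week 16 and stays outside the final efficacy results. Safety stops may differ between arms, so the choice should be made openly and before unblinding.

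**Working it through.** **The plan's own figure.** Inputs from SAP 5.1: means -15 and -8, SD 8, two-sided alpha 0.0167, 40 per group. Noncentrality = 7 / (8 × √(2/40)) = 3.91. The two-sample t-test power is 92.6%, which agrees with the stated 92%. At 46 per group it is 95.9%. These figures are not in dispute and serve only as a scale.

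**Window limits (SAP 5.4).**

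| Visit | Target day | Window | Upper limit minus target |
|---|---|---|---|
| Week 2 | 14 | 2-20 | 6 |
| Week 4 | 28 | 21-34 | 6 |
| Week 8 | 56 | 35-62 | 6 |
| Week 12 | 84 | 63-87 | 3 |
| Week 16 | 112 | 88 onward | open |

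**Late Week 12 visit.** Day 88 is 88 - 84 = 4 days from the Week 12 target and 112 - 88 = 24 days from the Week 16 target, yet it maps to Week 16. The midpoint of the two targets is Day 98. A visit within the protocol's ±2 days falls on Day 82-86 (or 83-87 if Week 12 is counted as Day 85) and stays in Week 12, so only an out-of-window visit is affected. The documents give no rate of late visits. If 2-8% fell on Day 88 or later (assumed), 0.02 × 46 = 0.9 to 0.08 × 46 = 3.7 values per arm would move.

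**Follow-up after a safety stop.** Put the follow-up at stop day S + 28 and read off the window:
- Week 8 needs 35 ≤ S + 28 ≤ 62, so S = Day 7-34 (28 days).
- Week 12 needs 63 ≤ S + 28 ≤ 87, so S = Day 35-59 (25 days).
- Stops on Day 1-6 map to Week 4, and stops on Day 60-84 to Week 16.
- With S + 26 the Week 12 range is Day 37-61; with S + 30 it is Day 33-57.

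At S + 28 the ET visit and the follow-up never share a window, so the closest-to-target rule does not remove the follow-up value. Subjects who meet the criteria in protocol 4.4.2 are withdrawn, so no regular Week 12 visit competes. With the half-life of 7.3-13.7 h from protocol 2.1.2, four weeks is 28 × 24 / 13.7 = 49 to 28 × 24 / 7.3 = 92 half-lives, so the value is off drug.

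**Size.** The documents give no safety-stop rate. Assume that 2-15% of an active arm stops for safety, evenly over 84 days, and that the whole 7-point effect is gone by the follow-up.
- Share of the arm with an off-drug Week 12 value: 0.02 × 25/84 = 0.6% to 0.15 × 25/84 = 4.5%, or 0.3 to 2.5 of 55 subjects.
- Shrinkage of the difference: 7 × 0.006 = 0.04 to 7 × 0.0446 = 0.31 points.
- Power at 46 per group: 95.9% falls to between 95.6% and 94.0%.

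**The case against.** Since 5.7 names only unscheduled and ET data, the natural reading may be that scheduled visits keep their nominal label, and then the Day 88 problem does not arise. That reading is possible, but 5.4 speaks of the efficacy endpoints in general, and its tie rule in favour of the scheduled result points to scheduled visits passing through the windows. The sections must be reconciled either way.

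A tighter upper limit at Week 12 can also be defended, because treatment lasts at most 12 weeks. Unequal tolerances are indeed not a defect in themselves. The difficulty is the consequence: a visit 4 days late is called Week 16.

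On the follow-up visit, most of the objection stands. The visit is planned in the protocol and is distinct from ET, so its re-mapping under 5.7 is an inference. If the database labels it as follow-up and labels are kept, it never reaches Week 8 or Week 12, and the SAP 6.3 statement fits that intention. If it is mapped, the mITT principle of analysis as randomized supports keeping a value observed at that time since randomization. Subjects who started a prohibited medication are already handled by SAP 6.2 in the primary analysis, although its sensitivity analysis brings their later values back.

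A reader might infer something stronger: that the Week 12 value of safety stops in general is a post-washout measurement, and that this moves an arm mean by 0.5-1.1 points. The documents do not support that. Only stops on about Day 35-59 qualify. The larger figure needs 5-10% of an arm to stop for safety in those 25 days, whereas even if all of the planned 15% dropout were safety stops spread evenly, the share would be 4.5%. It also needs relapse to about -4, which is worse than the planned placebo mean of -8.

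**Conclusion.** The main point holds as a correctable flaw in a stated rule. Applied as written, SAP 5.4 removes a late scheduled Week 12 visit from the primary time point when it falls on Day 88 or later, and SAP 5.7 leaves open whether that is meant. It touches only visits outside the protocol's ±2 days, and their number is unknown.

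The second point is an unstated choice and not an error. An EASI about four weeks after a safety stop on about Day 35-59 (or Day 7-34) can become the Week 12 (or Week 8) value, and SAP 6.2 does not address it unless a prohibited medication was started. Including or excluding it is a decision about the estimand. Under the assumptions shown, the effect on the primary difference is about 0.04-0.31 of 7 points. Neither point threatens the trial's power, but both concern which value enters the primary model.

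**What to change.** In SAP 5.4 and 5.7:

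1. State that a scheduled Week 12 visit keeps its nominal label. Alternatively, set the Week 12 window to Day 63-90 and start Week 16 at Day 91, which gives the same +6 days as the other windows. Say in both sections whether scheduled visits are re-mapped.
2. State before unblinding how the extra follow-up visit after a safety stop is labelled: by study day, or as post-treatment follow-up outside Weeks 2-12. Run the primary MMRM the other way as a sensitivity analysis, with or without these off-drug values.

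The cost is a few sentences, derivation code and one added model run; no study procedure changes. The small downside of item 1 is that a few Week 12 values taken some days after the last dose are kept. This does not prejudge item 2, because a visit a few days late is a different case from one four weeks after stopping.

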3.2 Schedule of Events

Table 1 provides a description of the procedures planned at each visit.

Table 1: Schedule of Events

Study Visits	Screening	Treatment Period					Follow-up / ET ¹² Week 16
		Day 1	Week 2	Week 4	Week 8	Week 12	
Window (days)	-30 to -1		±1	±2	±2	±2	±2
Informed consent	X						
Demographics	X						
Medical and surgical history	X	X					
Inclusion-exclusion criteria	X	X					
Pregnancy test ¹	X	X	X	X	X	X	X
Physical examination	X	X		X ³		X	X ³
Vital signs ²	X	X	X	X	X	X	X
ECG ⁵	X	X		X		X	X ⁴
Clinical laboratory tests (hematology, chemistry, and urinalysis)	X	X		X		X	X
Serology (HIV, HBV, HCV)	X						
Tuberculosis evaluation ⁶	X						
BSA	X	X	X	X	X	X	X
IGA	X	X	X	X	X	X	X
EASI	X	X	X	X	X	X	X
SCORAD		X	X	X	X	X	X
Pruritus NRS		X	X	X	X	X	X
5-D pruritus scale		X	X	X	X	X	X
DLQI		X	X	X	X	X	X
POEM		X	X	X	X	X	X
Skin biopsies collection ⁷	X		X ⁹			X	X ⁴
Blood sampling for PD analyses ⁸		X		X ⁹		X	X ⁴
Blood sampling for PK evaluation		X ¹⁰	X ¹¹	X ¹⁰	X ¹¹	X ¹¹	X ^{4,11}
Randomization		X					
Study product administration at study center		X	X	X	X		
Study product administration daily ¹³		X-----X					
Emollient use		X-----X					
Daily subject diary ¹⁴		X-----X					

	STATISTICAL ANALYSIS PLAN, Version Final 2.0
Protocol Number: ASN002AD-201 V3.0	Sponsor: Asana BioSciences, LLC

Study Visits	Screening	Treatment Period					Follow-up / ET ¹²
		Day 1	Week 2	Week 4	Week 8	Week 12	
Window (days)	-30 to -1		±1	±2	±2	±2	±2
Dispensing of study product		X		X	X		
Collecting of study product				X	X	X	X ⁴
Study product accountability/compliance			X	X	X	X	X ⁴
Verification of subject diary		X	X	X	X	X	X
Photograph AD area ¹⁵		X		X		X	X
Concomitant medication	X	X	X	X	X	X	X
Adverse events evaluation	X	X	X	X	X	X	X

BSA=body surface area; DLQI=Dermatology Life Quality Index; EASI=Eczema Area and Severity Index; ECG=electrocardiogram; ET=early termination; HBV=hepatitis B virus; HCV=hepatitis C virus; HIV=human immunodeficiency virus; IGA=Investigator Global Assessment; NRS=numeric rating scale; PD=pharmacodynamic; PK=pharmacokinetics; POEM=Patient-Oriented Eczema Measure; SCORAD=SCORing Atopic Dermatitis.

¹ Females of childbearing potential only. Serum pregnancy test at screening and urine pregnancy test at other visits.

² Including height, weight and BMI. Height will be measured only at screening and the same value will be used for BMI calculation at other visits.

³ Brief physical examinations.

⁴ Only at ET

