⁵ ECG will be recorded at 0 (pre-dose, within 1 hour of dosing), 1 (\pm 30 min), and 3 (\pm 1 hour) hours post-dose on Day 1 and Week 4. ECG will be recorded only once at screening, Week 12, and ET visits.

⁶ If PPD is used, a second screening visit will be necessary.

⁷ Optional, only for a subset of approximately 68 subjects who consent: two 4.5-mm skin biopsies at Day 1 (one from lesional skin and one from adjacent nonlesional skin) and one at Week 12/ET (from lesional skin). Subjects consenting to biopsies collection must also consent to PD samples. Biopsies should be collected prior to study product administration.

⁸ Optional, only for a subset of approximately 68 subjects who consent: PD samples to be drawn as trough samples prior to study product administration. Subjects consenting to PD samples must also consent to biopsies collection. PD samples should be collected prior to study product administration.

⁹ An additional skin biopsy from lesional skin and PD sample will be collected at Week 4 for subjects who consent to four biopsies.

¹⁰ PK samples will be collected at 0 (pre-dose), 1 (\pm 30 min), 3 (\pm 30 min), and 6 (between 5 to 12 hours post-dose) hours post-dose. The dosing time for the previous day should be recorded accurately.

¹¹ PK samples will be collected at 0 (pre-dose) and 2 (\pm 30 min) hours post-dose. The dosing time for the previous day should be recorded accurately. At ET and Week 12, only one PK sample will be collected.

¹² Follow-up visit for subjects not participating in the OLE study. Subjects who have their study product discontinued due to the start of a prohibited medication for the treatment of AD or for any other safety reasons will be asked to come back for an additional follow-up visit about 4 weeks after the study product discontinuation (in addition to the ET visit)..

¹³ Study products will be taken at home daily for 12 weeks, except on study visit days when the study products will be administered on site. No drug administration will be given at Week 12 visit as part of the present study.

¹⁴ Pruritus NRS, emollient use, time of study products administration, and fasting conditions will be recorded daily for 12 weeks in a subject diary. Pruritus NRS and emollient use will be recorded daily in a diary up to Week 16

	STATISTICAL ANALYSIS PLAN, Version Final 2.0
Protocol Number: ASN002AD-201 V3.0	Sponsor: Asana BioSciences, LLC

Study Visits	Screening	Treatment Period					Follow-up / ET ¹²

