5.1 Sample Size

Using the following assumptions for the primary efficacy endpoint: a change-from-baseline in EASI at week 12 of at least -15 in the ASN002 dosing groups, a change-from-baseline of -8 in the placebo group, a common standard-deviation of 8, nominal alpha of 0.0167 for each comparison of interest, we would need 40 evaluable subjects per group in order to achieve a power of 92% on the primary efficacy endpoint.

Moreover, with 46 subjects per group, we would have 80% power to show a statistically significant difference between the higher dosing group and placebo in IGA responses (one of the key secondary efficacy endpoint), assuming a response of 37.5% vs. 11.1% in the higher dosing and placebo groups, respectively, using an alpha of 5%.

Thus, assuming about 15% dropout rate, 55 subjects per group will need to be enrolled in this trial for a total of 220 subjects in order to have a minimum of 46 subjects per group to evaluate efficacy with adequate power.

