Information for stratification factor will be taken from the Electronic Data Capture (EDC) database, and not the IWRS for primary analysis.

Sensitivity Analyses

An analysis of variance (ANOVA) will be performed, where the absolute change from baseline in EASI score at Week 12 will be the dependent variable, the treatment group and stratification factor (baseline disease severity) will be fixed effects. A supportive analysis with pooled site and pooled

	STATISTICAL ANALYSIS PLAN, Version Final 2.0
Protocol Number: ASN002AD-201 V3.0	Sponsor: Asana BioSciences, LLC

site-by-treatment interaction included as fixed factors in addition to the other factors listed above will be performed in order to study the impact of pooled site on efficacy. If the pooled site-by-treatment interaction is not statistically significant, it will be removed from the model.

An additional sensitivity analysis will be carried out on the change from baseline in EASI score at Week 12 where data from site 029 is excluded.

Distribution of residuals will be visually examined to determine whether substantial departures from normality and homogeneity of variance are apparent. If the data are inconsistent with the assumption of normality, a nonparametric analysis of variance will be performed.

Additional sensitivity analyses will be performed using the stratification factor as per IWRS database in the primary efficacy MMRM model described above and including all efficacy EASI data for these subjects (before and after the prohibited medication).

	STATISTICAL ANALYSIS PLAN, Version Final 2.0
Protocol Number: ASN002AD-201 V3.0	Sponsor: Asana BioSciences, LLC

Subgroup Analyses

An analysis of variance (ANOVA) will be performed, where the absolute change from baseline or the percent change from baseline in EASI score at Week 12 will be the dependent variable, the treatment group and stratification factor as per EDC (baseline disease severity, [EASI = 16.0-21.2] vs. [EASI = 21.3-29.9] vs. [EASI = \geq 30.0] and treatment-by-stratification factor will be fixed effects. Treatment effect per stratification factor subgroup will be presented as well as associated p-values.

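### Does counting early-termination EASI scores from Day 63–69 as Week 12 values call for new visit windows?

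*SAP*

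**What the plan says.** SAP 5.4 introduces its table with "Statistical Windows have been proposed for the efficacy endpoints of this study". Targets are Days 14, 28, 56, 84 and 112. The windows are Day 2–20 (Week 2), 21–34 (Week 4), 35–62 (Week 8), 63–87 (Week 12) and 88 to end of study (Week 16). Within a window, "If there is more than one assessment for a given timepoint and analysis visit, the assessment closest to the target day will be considered".

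SAP 5.7 applies this table to off-schedule efficacy data: "unscheduled measurements and ET visit assessments will be re-mapped according to the windowing conventions in section 5.4". For safety data the same section keeps ET as a separate visit.

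The primary endpoint is the Week 12 change from baseline in EASI, analysed by MMRM in the mITT population, with the per-protocol population as support (SAP 12.1). The other planned analyses are:

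- a Week 12 ANOVA, and the same with pooled site and its interaction;
- exclusion of site 029;
- a nonparametric analysis if the residuals require it;
- the MMRM with strata taken from the IWRS;
- the MMRM with EASI data after prohibited medication put back.

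Protocol 8.3.1 adds observed-case analyses. SAP 6.2 sets efficacy values after the start of prohibited medication to missing in the main analysis.

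Under footnote 12 of SAP Table 1, subjects whose product is stopped for prohibited AD medication or for safety "will be asked to come back for an additional follow-up visit about 4 weeks after the study product discontinuation", in addition to the ET visit.

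**The concern.** A subject who leaves the study on Day 63 has had nine weeks of treatment, one week past the Week 8 target and three weeks short of Week 12. Yet that score enters the primary analysis as Week 12. The tie-breaker in 5.4 works only inside a window, so it cannot send the value back to Week 8. The limits also look uneven at first sight: the Week 2/Week 4 boundary (Day 21) is the midpoint of its two targets, whereas Day 35 and Day 63 each fall 7 days before theirs (Days 42 and 70).

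The label feeds the MMRM, the ANOVA and the Week 12 responder tests, where a single re-mapped value fixes a subject's response status. If many such values existed, or if they differed by arm, the primary contrast would mix Week 9–10 scores with Week 12 scores and no planned output would show it.

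A side question is how to label the extra follow-up visit after a safety stop, since 5.7 names only unscheduled and ET values.

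**Working it through.** **1. The plan's figures reproduce.** SAP 5.1 assumes a change of at least -15 on ASN002, "a change-from-baseline of -8 in the placebo group, a common standard-deviation of 8", alpha 0.0167 and 40 evaluable subjects per group. Then 7 / (8 × √(2/40)) = 3.91, which gives two-sided power of 93.6% (normal) or 92.6% (noncentral t), against the stated 92%. For enrolment, 46 / 0.85 = 54.1, rounded up to 55. These inputs can be used below.

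**2. Which days are affected.**

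| Day | Days from Week 8 target (56) | Days from Week 12 target (84) |
|---|---|---|
| 63 | 7 | 21 |
| 66 | 10 | 18 |
| 69 | 13 | 15 |
| 70 | 14 | 14 |

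Seven days, 63–69, are labelled Week 12 while nearer Week 8. An on-time Week 12 visit (Day 84 ± 2) always displaces such a value, so it counts only for subjects with nothing closer to Day 84 in the window.

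**3. Whether the limits are uneven.** 14 + 7 = 21, 28 + 7 = 35 and 56 + 7 = 63. One rule gives all three lower limits. Day 21 is a midpoint only because Weeks 2 and 4 are 14 days apart. The SAP uses forward windows at these visits; it never adopts a midpoint rule and then departs from it.

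**4. How many values.** Assume dropout is even over 84 days.

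- Dropouts per arm: 55 × 0.15 = 8.25.
- On Day 63–69, all attending ET: 8.25 × 7/84 = 0.69 per arm, or 2.75 over four arms.
- ET attendance is voluntary (Protocol 5.3.1). At an assumed 75% or 50% it is 0.52 or 0.34 per arm.
- If only 160 of 220 are evaluable: 60/4 = 15 dropouts per arm, and 15 × 7/84 = 1.25.

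Values after prohibited medication are already missing, which lowers these counts.

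**5. How far the contrast moves.** The share of Week 12 values affected is 0.6875 / (46.75 + 0.6875) = 0.0145. Assume linear improvement and an average of 18 days early.

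- Active: 15 × 18/84 = 3.21 points per value; arm mean 3.21 × 0.0145 = 0.047.
- Placebo: 8 × 18/84 = 1.71 points per value; arm mean 1.71 × 0.0145 = 0.025.
- Contrast: 0.047 - 0.025 = 0.02 points, against a planned 7.

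Adverse scenarios, all assumed:

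- A full SD (8 points) of error per value in one arm only: 8 × 0.0145 = 0.12.
- The same 8 points in both arms, with 25% dropout on placebo and 10% on active: 8 × [1.146 / (41.25 + 1.146) - 0.458 / (49.5 + 0.458)] = 0.216 - 0.073 = 0.14.

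The standard error of the contrast is about 8 × √(2/46.75) = 1.65, so even 0.14 is under a tenth of it.

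**6. Responder tests.** If every affected subject in one arm had the wrong status, that arm's rate would move by 0.0145, or 1.5 percentage points. The planned IGA difference is 37.5 - 11.1 = 26.4 points.

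**7. What a midpoint boundary would do.** A Day 63–69 value would move to Week 8. There it competes with the scheduled visit (Day 54–58, at most 2 days from target) and loses under the closest-to-target rule. The subject's last measured EASI would drop out of the by-visit analysis, and Week 12 would rest on the missing-at-random assumption.

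**8. The extra follow-up visit.** SAP Table 1 places follow-up in the column headed Week 16, so that label is a fair reading. After an ET visit on Day 63–69, a visit 28 days later falls on Day 91–97, which is Week 16 by day as well. Only a stop on Day 35–59, with 5.4 applied by day, would bring it into Week 12: 8.25 × 25/84 = 2.46 dropouts per arm, or 0.25 to 0.61 if 10% to 25% of them are safety stops (assumed).

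**The case for a change.** The best case for a change is that a primary label should be accurate and its robustness shown, however small the effect. The seven days are closer to Week 8, the SAP's own tie-breaker prefers nearness to target, and no reason is given for opening Week 12 at Day 63. Week 16 opens 4 days after the Week 12 target and not 7, so the forward rule does not run through the whole table. MMRM is already the chosen method for missing observations, and a subject who leaves on Day 65 still contributes earlier visits. The per-protocol analysis is no clear safeguard: it requires evaluable primary data, and whether a Day 65 score qualifies under SAP 3.1 is open. The observed-case analysis concerns imputation and not windows. The edit would cost a table and one model run.

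Part of this stands. The label is loose for those days, and no planned analysis removes the values by design. But the Day 88 limit has no bearing on Day 63–69. Redrawing the boundary exchanges a measured late score for model-based handling, and neither choice is plainly better. An extra MMRM run without re-mapped ET values would be harmless. It would leave out at most 8.25 × 19/84 = 1.9 values per arm (Day 63–81, full attendance) and would not be expected to change a conclusion.

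**Conclusion.** No change is needed. The plan uses a prespecified forward window, the same for every arm. Its cost is an imprecise label on roughly 0.7 Week 12 values per arm, and its benefit is that a late observed score is kept. The contrast moves about 0.02 EASI points against a planned 7, and 0.14 in the adverse scenario. No direction of bias is shown, and the effect on power is negligible.

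These sizes rest on 15% dropout spread evenly over 84 days, full ET attendance, linear improvement and a Week 12 mean treated as a simple average. Lower attendance and the prohibited-medication rule reduce them. Dropout at 60 of 220 raises the count to 1.25 per arm without altering the conclusion. Heavy dropout concentrated in Weeks 9–10 and differing by arm would be a different matter, but nothing in the documents suggests it.

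The remaining gaps are ones analysts fill sensibly: scheduled visits keep their nominal label, since 5.7 re-maps only unscheduled and ET values, and the extra follow-up visit belongs with the Week 16 column.
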